#### **9.4.3 Vital Signs**

The vital signs data will be presented in a listing: systolic and diastolic blood pressure (mm Hg), body temperature ( $^{\circ}$ C), HR (beats per minute), and respiratory rate (breaths per minute).

#### **9.4.4 Ophthalmologic Examination**

The ophthalmologic examination data will be presented in a listing.

[figure not shown]

### 9.4.5 Physical Examination

Physical examination data will be presented in a listing.

## 10. LIST OF APPENDICES

### Appendix A: Schematic of Study Design

## Appendix B: Schedule of Assessments

Table 3-1 Study VX15-770-123: Screening

Event/Assessment	Screening Period (Day -28 to Day -1) 
Clinic visit	X
Informed consent/assent	X
Inclusion/exclusion criteria review	X
Demography	X
CFTR genotype 	X
Medical history	X
Prior and concomitant medications	X
Height and weight	X
Physical examination and vital signs 	X
Multiple breath washout 	X
Coagulation	X
Serum chemistry	X
Hematology	X
Urinalysis	X
Ophthalmologic examinations 	X
Immunoreactive trypsinogen 	X
Fecal sample collection 	X
Adverse events	Continuous from signing of ICF through end of study participation

 All Screening assessments must be completed before the Day 1 Visit. Subjects may be rescreened after discussion with, and approval from, the Vertex medical monitor or authorized designee (see Section 8.1.1.2).

 *CFTR* genotyping will be performed to confirm that the subject has the *G551D*, *G178R*, *S549N*, *S549R*, *G551S*, *G1244E*, *S1251N*, *S1255P*, or *G1349D* mutation in at least 1 *CFTR* allele to meet inclusion criteria. Results of the genotyping should be confirmed during the Screening Period. If the *CFTR* screening genotype result is not received before randomization, a previous *CFTR* genotype lab report may be used to establish eligibility. *Subjects who have been randomized and whose screening genotype does not confirm study eligibility must be discontinued from the study.*

 See Section 11.5.3.

 Subjects must complete the multiple breath washout (MBW) assessment at Screening. The subject will be considered a screen failure if the MBW assessment cannot be performed, i.e., if 2 technically acceptable MBW tests are not achieved at the Screening Visit (or Rescreening Visit; see Section 8.1.1.2.). At least 3 MBW tests will be performed (see Section 11.4.1 and the Study Reference Manual).

 An OE will be conducted by a licensed ophthalmologist or optometrist (Section 11.5.6). The examination does not need to be repeated if there is documentation of an OE meeting protocol criteria that was conducted within 3 months before the Screening Visit. Subjects with documentation of bilateral lens removal do not need the OE.

 A blood sample for immunoreactive trypsinogen assessment will be collected.

 A stool sample for fecal elastase-1 [REDACTED] analysis will be collected (see Sections 11.4.7 [REDACTED] [REDACTED] for details). The stool sample to be collected at Screening may be collected at any time from Screening until before the first dose at Day 1.

Table 3-2 Study VX15-770-123: Part 1 and Part 2

		Part 1 Placebo-controlled Crossover Period 															
Treatment Period 1 (Day 1 to Wk 8)		Wash-out	Treatment Period 2 (Wk 16 to Wk 24)						Part 2 Open-label Period  (Wk 24 to Wk 144)								
Event/Assessment	Day 1	Wk 4	Wk 8	8 Wks	Wk 16	Wk 20	Wk 24	Wk 36	Wk 48	Wk 60	Wk 72	Wk 84	Wk 96	Wk 108	Wk 120	Wk 132	Wk 144
	(± 3 days)	(± 5 days)	(± 5 days)	(± 5 days)	(± 3 days)	(± 3 days)	(± 5 days)	(± 2 wks)	(± 2 wks)	(± 2 wks)	(± 2 wks)	(± 2 wks)	(± 2 wks)	(± 2 wks)	(± 2 wks)	(± 2 wks)	(± 2 wks)
Clinic visit	X	X	X		X	X	X	X	X	X	X	X	X	X	X	X	X
Inclusion/exclusion criteria review	X																
Randomization 	X																
Concomitant medications	X	X	X		X	X	X	X	X	X	X	X	X	X	X	X	X
Concomitant treatments and procedures	X	X	X		X	X	X	X	X	X	X	X	X	X	X	X	X
Height and weight	X	X	X		X	X	X	X	X	X	X	X	X	X	X	X	X

Notes: Subjects may complete their assessments over a period of 2 days at the Day 1 and Week 96 Visits. On the Day 1, Week 16, and Week 24 Visits, all assessments must be completed before dosing with study drug. Symptom-directed physical examinations and symptom-directed vital signs can be performed if deemed necessary by the investigator or healthcare provider (see Section 11.5.3).

 Subjects who prematurely discontinue study drug treatment (for any reason other than early study termination) will undergo the listed assessments at their Early Termination of Treatment Visit (see Table 3-3), which is to be scheduled as soon as possible after the subject decides to terminate study drug treatment. Subjects who prematurely discontinue treatment will also be required to complete the Safety Follow-up Visit, approximately 4 weeks (± 7 days) after their last dose of study drug. If the Early Termination of Treatment Visit occurs 3 weeks or later following the last dose of study drug, then the Early Termination of Treatment Visit will replace the Safety Follow-up Visit, and a separate Safety Follow-up Visit will not be required (see Section 8.1.7).

 Randomization will occur after all inclusion and exclusion criteria are met. If the screening genotype result is not received before randomization, a previous CFTR genotype lab report may be used to establish eligibility. *Subjects who have been randomized on the basis of a historical genotype lab report and whose screening genotype does not confirm study eligibility must be discontinued from the study.*

Table 3-2 Study VX15-770-123: Part 1 and Part 2

		Part 1 Placebo-controlled Crossover Period 															
Treatment		Treatment Period 2 (Wk 16 to Wk 24)							Part 2 Open-label Period  (Wk 24 to Wk 144)								
Period 1 (Day 1 to Wk 8)		Wash-out	Wk 4	Wk 8	Wk 16	Wk 20	Wk 24	Wk 36	Wk 48	Wk 60	Wk 72	Wk 84	Wk 96	Wk 108	Wk 120	Wk 132	Wk 144
		(± 5 days)	(± 3 days)	(± 3 days)	(± 5 days)	(± 2 wks)	(± 2 wks)	(± 2 wks)	(± 2 wks)	(± 2 wks)	(± 2 wks)	(± 2 wks)	(± 2 wks)	(± 2 wks)	(± 2 wks)	(± 2 wks)	(± 2 wks)
Day 1		X	X	X	X	X	X	X	X	X	X	X	X	X	X	X	X
Multiple breath washout 		X	X	X	X	X	X	X	X	X	X	X	X	X	X	X	X
Serum chemistry 		X	X	X	X	X	X	X	X	X	X	X	X	X	X	X	X
Hematology		X	X	X	X	X	X	X	X	X	X	X	X	X	X	X	X
Ophthalmologic examinations									X								
Immunoreactive trypsinogen 		X	X	X	X	X	X	X	X	X	X	X	X	X	X	X	X
Fecal sample collection 		X	X	X	X	X	X	X	X	X	X	X	X	X	X	X	X

 At least 3 MBW tests will be performed (see Section 11.4.1 and the Study Reference Manual). The assessment will be performed before the spirometry

 Liver function testing (alanine aminotransferase, aspartate aminotransferase, gamma-glutamyltranspeptidase, alkaline phosphatase, and total bilirubin) must be performed at the scheduled visits and at a minimum of every 4 weeks only for subjects who meet protocol-defined criteria for study drug interruption or discontinuation (see Section 11.5.2). For these subjects, liver function tests (LFTs) must be monitored at least every 4 weeks and can return to monitoring at regularly scheduled study visits when LFT results have returned to the subject's baseline and remain at baseline values for 8 weeks. Although blood samples will be collected and analyzed at a central laboratory, a local laboratory may be used if a subject cannot return to the clinical study site for liver function testing (see Section 11.5.2).

 A blood sample for immunoreactive trypsinogen assessment will be collected.

 A stool sample for fecal elastase-1 analysis will be collected (see Sections 11.4.7 for details).

Table 3-2 Study VX15-770-123: Part 1 and Part 2

		Part 1 Placebo-controlled Crossover Period 														
		Treatment Period 2 (Wk 16 to Wk 24)								Part 2 Open-label Period  (Wk 24 to Wk 144)						
Treatment Period 1 (Day 1 to Wk 8)		Wash-out	Wk 16	Wk 20	Wk 24	Wk 36	Wk 48	Wk 60	Wk 72	Wk 84	Wk 96	Wk 108	Wk 120	Wk 132	Wk 144	
Event/ Assessment	Day 1	8 Wks (± 5 days)	(± 3 days)	(± 3 days)	(± 5 days)	(± 2 wks)	(± 2 wks)	(± 2 wks)	(± 2 wks)	(± 2 wks)	(± 2 wks)	(± 2 wks)	(± 2 wks)	(± 2 wks)	(± 2 wks)	
Meal or snack at study center. 	X	X	X	X	X	X	X	X	X	X	X	X	X	X	X	
Study drug dosing at study visit 	X	X	X	X	X 	X	X	X	X	X	X	X	X	X	X	
Dispense study drug 	X	X	X	X	X	X	X	X	X	X	X	X	X	X	X	
Study drug count	X	X	X	X	X	X	X	X	X	X	X	X	X	X	X	
Continuous from signing of ICF through end of study participation																

 Study drug (placebo or Kalydeco) will be administered from Day 1 to the dose before the planned Week 24 Visit. Study drug should be administered every 12 hours, with fat-containing food (see Section 10.2). At the scheduled visits indicated, this meal or snack will be provided at the clinic to subjects after all predose assessments have occurred. Although subjects will not be dosed with study drug at the Week 8 or Week 144 Visits, a meal or snack will be provided. All subjects will be treated with Kalydeco during Part 2.

 Study drug will not be administered at the Week 8 Visit of Treatment Period 1. The last dose of study drug in Treatment Period 1 is the dose of study drug before the Week 8 Visit.

 The first dose of Kalydeco in the Open-label Period will be administered at the Week 24 Visit. Kalydeco dosing will continue to the dose before the planned Week 144 Visit.

 Study drug will be assigned through an interactive voice or web response system.

*Table 3-3 Study VX15-770-123: Early Termination of Treatment Visit, Safety Follow-up Visit, and Follow-up Telephone Contact*

Event/Assessment	Early Termination of Treatment Visit	Safety Follow-up Visit 4 weeks (±7 days) After Last Dose of Study Drug	Follow-up Telephone Contact 4 weeks (±7 days) After the Week 144 Visit
Clinic visit	X	X	
Telephone Contact			X
Concomitant medications	X	X	
Concomitant treatments and procedures	X	X	
Height and weight	X	X	
Serum chemistry	X	X	
Hematology	X	X	
Ophthalmologic examinations 	X		
Study drug count	X		
Adverse events	Continuous from signing of ICF through end of study participation		

 If the subject prematurely discontinues study drug treatment (for any reason other than early study termination), an Early Termination of Treatment Visit should be scheduled as soon as possible after the subject decides to terminate study drug treatment. Subjects who prematurely discontinue treatment will also be required to complete the Safety Follow-up Visit, approximately 4 weeks (± 7 days) after their last dose of study drug. If the Early Termination of Treatment Visit occurs 3 weeks or later following the last dose of study drug, then the Early Termination of Treatment Visit will replace the Safety Follow-up Visit, and a separate Safety Follow-up Visit will not be required (see Section 8.1.7).

 Subjects who discontinue study drug treatment will have an OE that is to occur between their last dose of study drug and completion of the Early Termination of Treatment Visit.

## Appendix C: Visit Window Mapping Rules for Efficacy and Safety Measurements

*Table 10-4 Visit Window Mapping Rules (within Period)*

Assessments	Period - Visit	Analysis Visit	Target Study Day	Visit Window (in study days)

 
• Labs               
 
○ Chemistry
 
○ Hematology
 
○ Liver Function Tests
 
○ Weight, Height.
 
 
 
	1 - Day 1	Day 1	1	[1, 1]
	1 - Week 8	Week 8	57	[2, 85]
	2 - Week 16	Day 1	1	[1, 1]
	2 - Week 24	Week 8	57	[2, Date of Week 24 visit]
	2 – Safety Follow-up Visit	Safety Follow-up Visit	NA	Use the nominal visit name

 
• LCI
 
	1 - Day 1	Day 1	1	[1, 1]
	1 - Week 4	Week 4	28	[2, 42 ]
	1 - Week 8	Week 8	57	[43, 85]
	2 - Week 16	Day 1	1	[1, 1]
	2 - Week 20	Week 4	28	[2, 42 ]
	2 - Week 24	Week 8	57	[43, Date of Week 24 visit]
	2 – Safety Follow-up Visit	Safety Follow-up Visit	NA	Use the nominal visit name

## Appendix D: Imputation Rules for Missing or Partial AE Dates

For missing or partial AE start date, use the imputation rules below for the purpose of determining whether an AE is treatment-emergent. The imputed dates will not be displayed in the listing outputs.

### If only Day of AE start date is missing:

If the AE start year and month are the same as that for the first dose date, then:

- If the full (or partial) AE end date is NOT before the first dose date or AE end date is missing, then impute the AE start day as the day of first dose date; otherwise, impute the AE start day as 1.
- Otherwise, impute the AE start day as 1.

Compare the imputed AE start date with TE period to determine whether the AE is pretreatment AE, TEAE or post-treatment AE.

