**Treatment Emergent (TE) Period:**

- For Treatment Period 1 of Part 1, the TE period will be from the first dose of study drug in Treatment Period 1 of Part 1 to the earliest of the following:
  - 1) 28 days after the date of subject's treatment completion during Treatment Period 1
  - 2) Safety Follow-up Visit if discontinued study early during Treatment Period 1
  - 3) 28 days after the last dose of the study drug for subjects who discontinued the study early during Treatment Period 1 and do not have a Safety Follow-up Visit
- For Treatment Period 2 of Part 1, the TE period will be from the first dose of study drug in the Treatment Period 2 of Part 1 to the earliest of the following:
  - 1) The date of treatment completion of Treatment Period 2
  - 2) Safety Follow-up Visit if discontinued study early during Treatment Period 2
  - 3) 28 days after the last dose of the study drug for subjects who discontinued the study early during Treatment Period 1 and do not have a Safety Follow-up Visit
- For Part 2, the TE period will be from the first dose of study drug in Part 2 to the earliest of the following:
  - 1) The Safety Follow-up Visit,
  - 2) 28 days after the last dose of the study drug for subjects who discontinued the study during Part 2 and do not have a Safety Follow-up Visit,

**Visit Windowing Rules:** Appendix C defines the windows for protocol-defined visits. The windows will be applied using the following rules for both scheduled and unscheduled visits. If no measurement is available within a visit window, the assessment will be considered missing for the visit. If there is more than one measurement available within the same visit window, the following rules will be used:

- For all safety parameters, if there are multiple measurements within a visit window, then 1) the record closest to the target day will be used, with the exception of the threshold analysis in which the worst record will be used; 2) if there are multiple records within the same distance of the target day, the latest record will be used; or 3) the Safety Follow-Up (SFU) visit will not be windowed; instead, the nominal visit will be used in relevant analyses.
- For all efficacy parameters, if there are multiple measurements within a visit window, the record at the scheduled visit will be used. Otherwise,
  - If there are no measurements at the scheduled visit, then the record closest to the target day will be used;

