### 9.4.1 Adverse Events

For analysis purposes, adverse events will be classified as pre-treatment emergent, TEAE, or post-treatment emergent. Adverse events which start (or increase in severity) during the period from the signing of informed consent up to, but not including, the first dose of study drug will be considered pre-treatment. Adverse events which start (or increase in severity) during the period from the first dose of study drug through completion of the Follow-up Visit will be considered TEAE. Adverse events which start (or increase in severity) after the completion of the Follow-up Visit will be considered post-treatment adverse events.

If an adverse event started (or increased in severity) during a specific treatment period, this adverse event will be attributed to the study drug the subject is receiving during this Treatment Period. Adverse events that started (or increased in severity) during the Washout Period and within 28 days of the last dose of treatment period 1 will be attributed to the treatment received in Treatment Period 1. Please see Section 9.1 for details.

For determining whether the AEs with missing or partially missing dates are treatment-emergent, please refer to Appendix D for rules. Please note that no imputation will be displayed in the listing outputs.

Adverse event summary tables will be presented for TEAE only and will include the following:

All TEAEs,

Related (defined as possibly related or related) TEAEs,

TEAEs leading to treatment discontinuation,

Serious TEAEs,

TEAEs by severity,

TEAEs by relationship.

Summaries will be presented by MedDRA system organ class and preferred term using frequency counts and percentages (i.e., number and percentage of subjects with an event). Subjects with multiple occurrences of the same adverse event or a continuing adverse event will be counted once, and only the maximum severity level will be presented in the severity summaries, and the worst/highest relationship level in the relationship summaries. In addition,

listing containing individual subject adverse event data for all deaths and other serious and significant adverse events will be provided, separately. All adverse events including Pre- and Post-treatment adverse events will be presented in individual subject data listings.

Imputation rules for missing or partial AE dates are presented in Appendix D.

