### If Day and Month of AE start date are missing:

If AE start year = first dose year, then:

- If the full (or partial) AE end date is NOT before the first dose date or AE end date is missing, then impute the AE start Month and Day as the Month and Day of first dose date; otherwise, impute the AE start Month as January and the Day as 1.
- Otherwise, impute the AE start MONTH as January and the DAY as 1.

Compare the imputed AE start date with TE period to determine whether the AE is pretreatment AE, TEAE or post-treatment AE.

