### If Year of AE start date is missing:

If the year of AE start is missing or AE start date is completely missing then query site with no imputation. Also compare the full (or partial) AE end date to the first dose date. If the AE end date is before the first dose date then the AE should be considered as a pretreatment AE.

Otherwise, the AE will be considered as TEAE.

Missing or partially missing AE end date will not be imputed.

**Appendix E: Threshold Analysis Criteria***Table 11-5 CRITERIA for POTENTIALLY CLINICALLY SIGNIFICANT EVENT*

Parameter	Threshold Criteria	Comments
Clinical Chemistry		
CPK	>ULN - $\leq 2.5$ x ULN >2.5 - $\leq 5$ x ULN >5 - $\leq 10$ x ULN >10 x ULN	CTCAE grades 1-4
Creatinine	>ULN - $\leq 1.5$ x ULN >1.5 - $\leq 3.0$ x ULN >3.0 - $\leq 6.0$ x ULN >6.0 x ULN	CTCAE grades 1-4
Blood Urea Nitrogen	>ULN - $\leq 1.5$ x ULN >1.5 - $\leq 3.0$ x ULN >3.0 - $\leq 6.0$ x ULN >6.0 x ULN	Same criteria as creatinine  No CTCAE
Sodium	Hyponatremia <LLN - $\geq 130$ mmol/L <130 - $\geq 120$ mmol/L <120 mmol/L  Hypernatremia >ULN - $\leq 150$ mmol/L >150 mmol/L - $\leq 155$ mmol/L >155 mmol/L - $\leq 160$ mmol/L >160 mmol/L	CTCAE grade 1, 3, 4  (No CTCAE grade 2)  CTCAE grade 1-4
Potassium	Hypokalemia <LLN - $\geq 3.0$ mmol/L <3.0 - $\geq 2.5$ mmol/L <2.5 mmol/L  Hyperkalemia >ULN - $\leq 5.5$ mmol/L >5.5 - $\leq 6.0$ mmol/L >6.0 - $\leq 7.0$ mmol/L >7.0 mmol/L	CTCAE grade 1&2, 3, 4  (Grade 1 and 2 are the same)  CTCAE grade 1-4
Total Cholesterol	>ULN - $\leq 7.75$ mmol/L >7.75 - $\leq 10.34$ mmol/L >10.34 - $\leq 12.92$ mmol/L >12.92 mmol/L	CTCAE grade 1-4
Triglycerides	>1.71 - $\leq 3.42$ mmol/L >3.42 - $\leq 5.7$ mmol/L >5.7 - $\leq 11.4$ mmol/L >11.4 mmol/L	CTCAE grade 1-4
Glucose	Hypoglycemia <3.0 - $\geq 2.2$ mmol/L <2.2 - $\geq 1.7$ mmol/L <1.7 mmol/L  Hyperglycemia >ULN - $\leq 8.9$ mmol/L >8.9 - $\leq 13.9$ mmol/L >13.9 - $\leq 27.8$ mmol/L >27.8 mmol/L	CTCAE grade 1-4  CTCAE grade 1-4

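### SAP Appendix D dates partial AE starts from a single first dose, so a day-missing Period 2 event in the Week 16 dose month usually lands in no treatment-emergent period; SAP 9.1 and 9.4.1 also disagree on late-washout events

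*SAP*

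**What the plan says.** SAP Appendix D says to "use the imputation rules below for the purpose of determining whether an AE is treatment-emergent". For a missing day the test is "If the AE start year and month are the same as that for the first dose date, then": the day becomes that of the first dose, unless the event ended earlier. In any other month, "otherwise, impute the AE start day as 1". For a missing day and month in the first-dose year, the rule is to "impute the AE start Month and Day as the Month and Day of first dose date", again unless the event ended earlier. The imputed date is then compared with the TE period. Appendix D does not say which first dose is meant. Its year-missing rule does point to one: "If the AE end date is before the first dose date then the AE should be considered as a pretreatment AE".

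SAP 9.1 defines TE periods separately. The Period 1 TE period runs at most to 28 days after Period 1 treatment is completed. For Period 2, "the TE period will be from the first dose of study drug in the Treatment Period 2 of Part 1".

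SAP 9.4.1 uses one continuous interval: an event "from the first dose of study drug through completion of the Follow-up Visit will be considered TEAE". It attributes an event to the treatment of the period in which it began, and a washout event "within 28 days of the last dose of treatment period 1 will be attributed to the treatment received in Treatment Period 1". It then refers to 9.1 for details. Protocol 12.3.5 and 12.3.5.1 define a TEAE as an event at or after first dosing, with no gap, and attribute it by onset date and the treatment being received then.

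**The concern.** A rule written around one dosing start is applied to a crossover with two. For an event near the first dose, Appendix D leans towards treatment-emergent. For an event near the second first dose, at Week 16, it moves the onset back to before the dose. The by-treatment TEAE tables could then lose a Period 2 event.

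The second problem needs no missing date. An event in the last four weeks or so of washout is a TEAE under 9.4.1 and the protocol, is in no TE period under 9.1, and is attributed to neither treatment. Two programmers following the SAP could produce different TEAE tables from the same data. Numbers are low (SAP 9.3.1 drops the mixed model for that reason), so a single event can be visible in a table.

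**Working it through.** The plan gives no figure to reproduce; this is date logic.

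**Inputs.** First dose on Day 1. The last Period 1 dose is the one before the Week 8 Visit (protocol 8.1.2), read as Day 56 or Day 57. The Period 1 TE period ends 28 days later (SAP 9.1), on Day 84 or 85. The washout is 8 weeks, plus or minus 5 days (protocol 8.1.3). The Week 16 dose is on nominal Day 113, range Day 108 to 118. Period 2 has 56 days.

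**Late washout outside both TE periods.** 113 − 85 − 1 = 27 days, or 113 − 84 − 1 = 28 days. With the window the range is 108 − 85 − 1 = 22 to 118 − 84 − 1 = 33 days.

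**Which branch applies.** The Week 16 dose comes 112 days after Day 1, so it is never in the first-dose month. A day-missing event in the Week 16 dose month is therefore always set to the 1st.

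**Example.** Day 1 is 1 September 2016 and the last Period 1 dose is 26 October (Day 56). The Period 1 TE period ends on 23 November and the Week 16 dose is on 22 December. A Period 2 event recorded as December 2016 becomes 1 December, which is in neither TE period.

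**Per subject.** If the Week 16 dose falls on day d > 1 of a month with L days, the share of Period 2 days imputed before that dose is (L − d + 1)/56. If d = 1 it is 0. With L = 31:

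| d | Share |
|---|---|
| 2 | 30/56 = 54% |
| 15 | 17/56 = 30% |
| 31 | 1/56 = 2% |

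Period 2 days in later months are set to a 1st that is already after the dose, so they are unaffected.

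**Averages.** Assume dose dates spread evenly over the year, onsets spread evenly over Period 2, and mean L = 365/12 = 30.4.

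- All day-missing Period 2 events imputed before the dose: (L − 1)/112 = 29.4/112 = 26.3%.
- Of those in the Week 16 dose month: (L − 1)/(L + 1) = 29.4/31.4 = 93.6%.

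A few of these reach back into the Period 1 TE period, when the Week 16 dose is on the 29th or later (Day 57 reading) or the 30th or later (Day 56 reading). Enumerating every first-dose date in a 365-day and a 366-day year puts these at 0.4 to 0.9% of events in the dose month. The share in no TE period is then:

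| | Week 16 dose month | All day-missing Period 2 events |
|---|---|---|
| Nominal schedule | 92.7 to 93.2% | about 26% |
| With ±5-day washout window | 87.0 to 93.6% | 24 to 26% |

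All these shares are conditional on a missing day.

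**The case against.** **First dose date could mean the first dose of the period concerned.** SAP 9.1 starts each TE period at its own first dose, and Appendix C maps visits within period. That reading would remove the first problem. But the year-missing rule ties the date to pretreatment status, and 9.4.1 defines pretreatment as before the first dose of study drug. A per-period reading also needs the period to be known, which a partial date may leave open. If it was intended, the SAP must say so.

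**A reader might infer that a true TEAE is lost by Appendix D's own comparison.** The documents do not establish that. The possible outcomes are pretreatment, TEAE and post-treatment. SAP 9.4.1 and protocol 12.3.5 keep an event after first dose and before follow-up as a TEAE. It ceases to be one only if 9.1 overrides 9.4.1, which is not stated for AEs. What is lost on the 9.4.1 reading is the treatment column.

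**A reader might also infer that year-only Period 2 events are charged to the wrong treatment.** About 85% of their imputed dates would fall in the Period 1 TE period. But Appendix D limits imputation to TE status, and no text says the imputed date also drives attribution. The event stays a TEAE; the rest is conjecture.

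**The effect is small.** This stands. Protocol 13.1.1.3 requires AE dates and asks about AEs at every visit, and 13.3 has missing data queried. SAP 9.4 makes safety descriptive with no testing, and 9.4.1 lists all AEs.

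**Conclusion.** Both points hold, as a minor correction. On the natural reading of Appendix D, a day-missing Period 2 event in the Week 16 dose month falls in no 9.1 TE period about 93% of the time. It is a TEAE without a treatment under 9.4.1 and the protocol, and not treatment-emergent under 9.1. Independently of any missing date or reading of first dose, 9.1 and 9.4.1 conflict over 22 to 33 days of late washout.

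The percentages rest on the even-spread assumptions and ignore Part 2. The number of partial dates is not in the documents and is probably small. No direction favouring either treatment is shown.

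A reader might take SAP 9.2.4, which calls medications between the TE periods post-treatment, as proof that late-washout AEs are meant to be off-treatment and not TEAEs. That rule covers medications only, and the protocol's AE definition has no such gap.

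**What to change.** 1. **Appendix D.** State that the pretreatment test uses the Period 1 first dose date. Where the known parts of a partial date match the month of the Week 16 dose, and the end date is missing or not before that dose, impute the Week 16 dose date. Every true Period 2 event in that month then falls in the Period 2 TE period. State that one date serves both TE status and treatment attribution, and flag imputed cases. Year-only dates still unresolved after query should be flagged, and not placed on Period 1 Day 1 for attribution.

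2. **SAP 9.1 and 9.4.1.** Reconcile both with protocol 12.3.5 and 12.3.5.1. Keep late-washout AEs as TEAEs and show them in a separate off-treatment washout column or row, under neither treatment. If they are instead to be excluded from TEAEs, declare that in SAP 3.1, which now records no modification from the protocol.

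The cost is SAP wording and a small programming change before database lock, with no new data. The downside is that some day-missing events that truly began in the late washout, in the same month as the Week 16 dose, will be counted in Period 2. The flag keeps them visible.
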